#### 15.3 Safety Run-In Phase

There is no significant published experience with SBRT used concurrently with CBI in this study population. Therefore, to ensure that the combination is safe, the first six patients will be treated and observed for toxicity for 30 days after radiation before continuing with further accrual. 6 patients will be enrolled at the proposed dose of CBI and SBRT. If  $\leq 3$  toxicity events occur in the first 6 patients within 30 days of therapy, we proceed with additional accrual with this regimen to complete a total of 146 patients. If  $\geq 4$  toxicity events occur among the first 6 patients, we will suspend the study pending data review.

*Toxicity Event:* ≥grade 3 adverse event (CTCAE v 4.0) with an attribution of possible, probable, or definite.

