# 1. PROTOCOL SYNOPSIS

TITLE	Randomized Phase II Study of Checkpoint Blockade Immunotherapy combined with Stereotactic Body Radiation Therapy in Advanced Metastatic Disease.
STUDY PHASE	Phase II
INDICATION	Patients who will receive CBI immunotherapy with at least 1 site of measurable metastatic disease which will not be irradiated.
PRIMARY OBJECTIVE	To determine whether SBRT combined with concurrent CBI improves the relative objective response rate (CR+PR) compared to CBI alone in patients with metastatic disease.
SECONDARY OBJECTIVES	
 
To assess the safety and toxicity of CBI used concurrently with SBRT delivered in 3 fractions in patients with metastatic disease
 
To determine the progression free survival, overall survival, and rate of stable disease greater than or equal to 6 months in patients after completion of SBRT in combination with CBI
 
To assess whether SBRT combined with concurrent CBI results in improvements in anti-tumor immune responses compared to CBI alone
 

HYPOTHESIS	Concurrent SBRT and CBI will increase the relative objective response (CR+PR) rate by at least 33% compared to CBI alone.
STUDY DESIGN	Patients who will receive CBI and have at least 1 site of measurable metastatic disease which will not be irradiated will be candidates for study. Patients will be randomized (1:1) to CBI combined with SBRT or CBI alone. SBRT at 9.5Gy x3 fractions will be delivered within 1-21 days of the start of Cycle #1 of CBI. The first six patients will be treated and observed for toxicity in the safety run-in phase for 30 days after radiation before continuing with further accrual. Radiation dose reduction is allowed if necessary to meet tissue constraints (6Gyx3 Minimum Dose). Response rates will be determined from the non-irradiated lesion/lesions and three blood draws will be obtained to analyze anti-tumor immune responses.
SAMPLE SIZE BY TREATMENT GROUP	73 patients per group (146 patients total)

SUMMARY OF SUBJECT ELIGIBILITY CRITERIA	
 
At least 1 site of measurable metastatic disease which will not be irradiated.
 
Plan to treat patient with CBI
 
Age ≥3 years.
 
Lansky scale score of ≥70 (ages ≥ 3 or < 16 years)         OR         Karnofsky scale score of ≥70 (ages ≥ 16 or < 18 years)         OR         ECOG performance status ≤ 2 (18 years or older).
 
Histologic confirmation of malignancy (primary or metastatic tumor).
 

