#### **6.2** Therapeutic Procedures

Patients will be pre-screened for eligibility and should be enrolled and randomized prior to starting immunotherapy. However, patients who have started immunotherapy up to 5 days prior to enrollment will be still be eligible for screening, randomization, and enrollment.

Upon confirmation of eligibility and enrollment in the study, the following will be completed:

- 1) Demographics review, medical history and clinical exam
- 2) Review of concurrent medications
- 3) Vital signs, height and weight
- 4) Laboratory Bloodwork including: CBC, BMP, LFT.
- 5) Plasma and Peripheral blood mononuclear cells will be collected and subsequently frozen for immune monitoring assays.
- 6) Tumor measurements (Recist 1.1) within 4 weeks prior to start of CBI

Upon randomization into the SBRT arm of the protocol, patients will be seen by at least one of the Co-Investigator Radiation Oncologists. CT simulation will be performed with fabrication of a radiation therapy immobilization device (such as a Vac-Lok) which will be custom made for each patient. The treating radiation

oncologist will identify the location of the tumor. Gross tumor volume (GTV) delineation will be performed on sequential axial computed tomography images. An SBRT treatment plan will be developed based on tumor size and location. The dose will be prescribed to the minimal isodose line that completely covers the GTV plus a 5 mm margin. Adjacent normal structures including but not limited to the chest wall, spinal cord, heart, esophagus, aorta, kidneys, rectum, bowel, liver, and stomach within 5 cm of the GTV will be identified for the purpose of limiting incidental radiation to these structures.

In addition, prior to treatment delivery, a four-dimensional cone beam CT study will be performed on individual patients to assess respiration in these patients and to determine tumor targeting accuracy for those tumors that may be subject to respiratory motion such as those in the lung, abdomen, or liver. If tumor motion is greater than 5 mm, the planning target volume (PTV) will be expanded to account for respiration.

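### The six-patient safety run-in is not reconciled with 1:1 randomisation, and if the six are assigned to SBRT nothing keeps them out of the randomised comparison

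*Combined protocol and SAP*

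**What the plan says.** **Run-in.** Section 15.3 states that "6 patients will be enrolled at the proposed dose of CBI and SBRT". If the toxicity count is acceptable, "we proceed with additional accrual with this regimen to complete a total of 146 patients". The synopsis says: "The first six patients will be treated and observed for toxicity in the safety run-in phase for 30 days after radiation", with further accrual waiting until that period is over.

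**Randomisation.** The synopsis says "Patients will be randomized (1:1) to CBI combined with SBRT or CBI alone" and gives the sample size as "73 patients per group (146 patients total"). Section 6.2 says "Patients will be pre-screened for eligibility and should be enrolled and randomized prior to starting immunotherapy", allowing only for patients who began immunotherapy up to five days earlier. It then describes SBRT planning as following randomisation to the SBRT arm. The schema footnote also speaks of patients being enrolled and randomised. None of these places makes an exception for the run-in.

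**Analysis.** Section 15.5 takes in registered subjects who received all three SBRT fractions. Section 15.8 bases the main response analysis and all conclusions on eligible patients. The population definitions in section 11.2 do not mention the run-in. No section excludes the six or reports them separately.

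**Counting rule.** Section 15.3 measures its 30 days from radiation in one sentence, but in another it refers to "toxicity events occur in the first 6 patients within 30 days of therapy". It suspends the study on a number of events: "toxicity events occur among the first 6 patients, we will suspend the study pending data review".

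**The concern.** Section 15.3 read literally and the 1:1 allocation cannot, in general, both be followed. If the first six patients enrolled all receive SBRT, they were almost certainly not randomised. If they were randomised, some will almost certainly be controls.

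The primary analysis is at stake. Six assigned patients would enter one arm only, recruited before any control and chosen by staff who knew what they would receive. Sections 15.5 and 15.8 would keep them in. Any difference between them and later patients in tumour type, CBI regimen or fitness would then be counted as an SBRT effect.

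The run-in itself is also affected. Which patients are counted decides when accrual pauses and how many patients have been enrolled by then.

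**Working it through.** **Inputs from the documents.** 146 patients, 73 per group (synopsis, 15.2); response rates of 61% and 81% for dual-agent treatment, one-tailed test, 80% power (15.2); six run-in patients (15.3). Section 15.2 prints the significance level as 0.05%; 5% is assumed here, so z = 1.645. The documents name no test for the primary comparison, so a pooled z test is used.

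**1. Reproducing 146.** With a mean rate of 0.71, n per arm = [1.645 × √(2 × 0.71 × 0.29) + 0.842 × √(0.61 × 0.39 + 0.81 × 0.19)]² / 0.20² = 62.6. The continuity correction gives (62.6/4) × [1 + √(1 + 4/(62.6 × 0.20))]² = 72.2. That rounds up to 73 per arm and 146 in total, the plan's figure. It contains no allowance for six extra patients.

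**2. Can both descriptions hold?** Under simple 1:1 randomisation, the chance that the first six enrolled all receive SBRT is (1/2)⁶ = 1/64 = 1.6%.

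**3. The six as the first six randomised to SBRT.** All patients are randomised, so there is no bias. Expected enrolment when the sixth SBRT patient enters is 6/0.5 = 12 (5th-95th percentile 7-18, simple randomisation). This differs from pausing after the first six.

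**4. The six as assigned patients.** If the other 140 are randomised 1:1, the arms are 76 and 70, and the six are 6/76 = 7.9% of the SBRT arm. If the arms are held at 73 and 73, they are 6/73 = 8.2%. If the six respond better by d, the SBRT-arm rate rises by d × 6/76 or d × 6/73. That is 0.8 points for d = 10 and 1.6 points for d = 20.

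Exact one-sided type I error follows from enumerating all outcomes. There is no true effect, every other patient responds at 61%, and the six respond at the rate shown:

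| Response rate of the six | 76/70, uncorrected | 73/73, uncorrected | 76/70, corrected | 73/73, corrected |
|---|---|---|---|---|
| 61% (no difference) | 4.7% | 5.3% | 3.3% | 3.7% |
| 71% (assumed) | 5.8% | 6.5% | 4.1% | 4.6% |
| 81% (assumed) | 7.0% | 7.8% | 5.0% | 5.6% |

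**5. Cost of excluding six assigned patients (61% vs 81%).** Corrected power at n per arm is Φ{[0.20 − 1/n − 1.645 × √(2 × 0.71 × 0.29/n)] / √[(0.61 × 0.39 + 0.81 × 0.19)/n]}.

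- n = 73: (0.20 − 0.0137 − 1.645 × 0.0751)/0.0733 gives 80.4%.
- n = 70: (0.20 − 0.0143 − 1.645 × 0.0767)/0.0748 gives 78.7%.
- Without the correction: 85.2% falls to 83.8%.
- If 67 SBRT and 73 control patients remain: 78.5% corrected, 83.7% uncorrected.
- Keeping 73 per arm randomised and adding the six needs 146 + 6 = 152 patients.

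**The case against.** The strongest reply is that the six are plainly the first six patients randomised to SBRT. Every description of enrolment includes randomisation, SBRT planning starts only after randomisation to that arm, and 73 per group fits full 1:1 allocation, whereas six assigned plus 140 randomised would give 76 and 70. The sentence about the dose of CBI and SBRT could describe a cohort within one arm, since controls are not enrolled at that dose. Much of this stands: it is the better-supported reading and carries no bias. But the plan does not say it, and it does not fit the first-six wording or a pause after six.

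The 10- and 20-point differences have no source in the documents, and the six meet the same eligibility criteria as everyone else. That also stands: the type I error figures are illustrations. With a continuity-corrected test, error passes 5% only in the 20-point case with 73 per arm.

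A reader might go further in three ways that the documents do not support:

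- **That the primary comparison is biased as planned.** This follows only if the six are assigned, which the text does not establish.
- **That the run-in would include controls and so barely test the combination.** The sentence placing six patients on CBI and SBRT, and a window that starts from radiation, nearly exclude this.
- **That 15.3 and 15.4 conflict because one counts events and the other uses a proportion.** They are separate rules: a one-time check of grade 3 or higher events, and continuing monitoring of grade 4/5 toxicity by site. They may use different units.

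**Conclusion.** The concern holds as an unreconciled contradiction with a conditional consequence. Section 15.3 and the 1:1 allocation agree with probability of only about 1.6% under simple randomisation, and nothing in the visible text settles which governs. The schema figure is not shown and might do so.

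On the favoured reading there is no bias, only wording that would pause accrual at a different point from the one intended. On the literal reading, about 8% of the SBRT arm is non-randomised, and one-sided type I error rises by roughly 1 point for an assumed 10-point difference and by 2 to 2.5 points for an assumed 20-point difference (uncorrected z test, 61% elsewhere, 5% level assumed). That is modest, but it affects the primary comparison and is avoidable. The point should be fixed; confidence is medium because the intended allocation is unknown.

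**What to change.** The sponsor should reconcile section 15.3 and the synopsis with the 1:1 randomisation by stating whether the six are randomised and which patients count towards the run-in.

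If they are assigned, sections 15.5 and 15.8 should each say that they are reported separately and excluded from the randomised comparison. The randomised total and its power should then be restated: 140 within the 146, or 146 plus six.

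Within section 15.3, the sponsor should also reconcile the two 30-day wordings and say whether the rule counts events or patients. Which cohort, unit, threshold or window applies is for the sponsor to decide; none is proposed here.

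The cost is wording only if the six are randomised. If they are assigned, it is about 1-2 points of power, or six more patients.

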#### 15.4 Early Stopping Guidelines:

This study will monitor site-specific grade 4/5 toxicity. If it becomes evident that the proportion of grade 4/5 toxicity at specific sites convincingly exceeds 30%, the study will be halted for a safety consultation. Specifically, we will apply a Bayesian toxicity monitoring rule that suspends the enrollment if the posterior probability of toxicity being larger than 30% threshold is 75% or higher.

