#### 7.2.2 Safety Profiles

#### 7.2.2.1 Nivolumab

Patients have received nivolumab at doses of 0.1, 0.3, 1, 3, 10, or 20 mg/kg intravenously every 2 weeks with no maximal tolerated dose identified[85]. The incidence, severity and relationship of AEs are generally similar across dose levels and tumor types. Nivolumab related AEs of any grade occur in approximately 75% of subjects[85]. The most frequently reported AEs are fatigue (54.9%), decreased appetite (35.0%), diarrhea (34.3%), nausea (30.1%), and cough (29.4%). Most treatmentrelated AEs are low grade. Treatment-related high grade (Grade 3-4) AEs have been reported in approximately. 17.0% of subjects. The most common treatment-related high grade AEs are fatigue (2.3%) and diarrhea (1%). Drug-related SAEs have been reported to occur in approximately in 11% of subjects. Select AE categories include: GI AEs, pulmonary AEs, renal AEs, hepatic AEs, skin AEs, and endocrinopathies. Patients who receive 10 mg/kg have had a numerically greater frequency of high-grade select AEs including the subcategories of endocrinopathies, GI, pulmonary, and infusion reaction. High grade events have been reported to resolve following the treatment guidelines for the treatment of pulmonary events, GI events, hepatic events, renal events, and endocrine events, respectively. Treatment-related AEs leading to discontinuation have been reported in 10.5%, the most frequent of these were pneumonitis (2.6%) and colitis (1.0%)[85].

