#### 11.2 Definitions

Evaluable Population: will consist of all patients who have received at least 1 cycle of CBI with or without SBRT.

Safety Population: Will consist of all subjects who were enrolled and have received at least 1 cycle of CBI with or without SBRT. This will be used to assess the clinical safety and tolerability of the study.

Evaluable for Objective Response: Patients who have measurable disease present at baseline and have received at least 1 cycle of CBI, and have had their disease re- evaluated will be considered evaluable for response. These patients will have their response classified according to the definitions stated below.

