#### 15.7 Evaluation of Toxicity

All patients will be evaluable for toxicity from the time of their first treatment of CBI.

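### The Section 15.4 grade 4/5 stopping rule leaves site, arm and denominator undefined, so it does not reliably test whether SBRT plus CBI exceeds the plan's own 30% limit

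*Combined protocol and SAP*

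**What the plan says.** Section 15.4 opens with "This study will monitor site-specific grade 4/5 toxicity". It continues: "If it becomes evident that the proportion of grade 4/5 toxicity at specific sites convincingly exceeds 30%, the study will be halted". The trigger is Bayesian: it "suspends the enrollment if the posterior probability of toxicity being larger than 30% threshold is 75% or higher". The section gives no definition of site, no arm, no denominator, no prior, no first look and no look schedule.

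Elsewhere, the safety denominators cover both arms. Section 11.2 defines the safety population: "Will consist of all subjects who were enrolled and have received at least 1 cycle of CBI with or without SBRT". Section 15.7 adds: "All patients will be evaluable for toxicity from the time of their first treatment of CBI". The Synopsis makes half of these patients controls: "Patients will be randomized (1:1) to CBI combined with SBRT or CBI alone", with 73 per group.

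The only numerical rule explicitly tied to the combination is the run-in in Section 15.3. It covers six patients for 30 days and suspends the study at four or more attributable events of grade 3 or higher.

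**The concern.** The safety question in this trial is whether adding SBRT to CBI is too toxic. Section 15.3 itself says that there is little published experience with the combination. A rule that answers the question needs the patients who received SBRT as its denominator and any grade 4/5 event as its numerator. Section 15.4 states neither.

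Two mechanisms could then hide harm. Including controls dilutes the rate. Comparing each organ separately with 30% means that toxicity spread over several organs is never added up. A third reading, by irradiated site, removes both mechanisms but cuts the SBRT arm into small groups in which chance alone can cross the boundary. Two monitors could apply this wording in good faith and reach opposite decisions on the same data.

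**Working it through.** **Plan's own figure.** There is none to reproduce. Section 15.4 gives no boundary, error rate or operating characteristic.

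**Inputs from the documents.** Limit 30% and posterior trigger 75% (Section 15.4); 73 per arm, 1:1 (Synopsis).

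**Assumptions.**
- True grade 4/5 rates: 45% with SBRT and 10% with CBI alone. The documents give neither. The nearest anchor is for nivolumab and is not grade 4/5 (Section 7.2.2.1): "Treatment-related high grade (Grade 3-4) AEs have been reported in approximately. 17.0% of subjects". A 17% control rate is therefore shown as well.
- Looks every 10 enrolled patients.
- Priors Beta(1,1), Beta(0.3,0.7) and Beta(3,7).
- For the organ reading: the 45% falls evenly on three organs (15% each), one event per patient.

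**Formula.** With prior Beta(a,b) and x events in n patients, suspend when Pr(p > 0.30) ≥ 0.75, where p ~ Beta(a+x, b+n−x).

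**Boundaries at full accrual.**
- Pooled, n = 146, Beta(1,1): x = 47 gives Beta(48,100) and Pr = 0.732 (continue); x = 48 gives Beta(49,99) and Pr = 0.787 (suspend).
- SBRT arm, n = 73, Beta(1,1): x = 24 gives Beta(25,50) and Pr = 0.724 (continue); x = 25 gives Beta(26,49) and Pr = 0.800 (suspend).
- The boundaries 48/146 and 25/73 are the same under the other priors.

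**Dilution by pooling.** The pooled true rate is (0.45 + 0.10)/2 = 27.5%, below the limit. At full accrual with 7/73 control events (9.6%), the SBRT arm can have 47 − 7 = 40 events, that is 40/73 = 55%, without crossing. With 12/73 control events (16.4%) it can have 35/73 = 48%.

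**Splitting by organ.** At 15% per organ, the expected count is 0.15 × 73 = 11 events, against a boundary of 25.

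**Splitting by irradiated site.** Under Beta(1,1), one event in the first patient at a site gives Beta(2,1) and Pr = 1 − 0.30² = 0.91, which already exceeds 0.75.

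**Probability of suspending at some look (simulation, looks every 10 patients, range over the three priors).**

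| Reading of Section 15.4 | True rate with SBRT | Trials suspended |
|---|---|---|
| Any site, SBRT arm | 45% | about 99% |
| Any site, arms pooled (controls 10%) | 45% | 32-47% |
| By organ, SBRT arm | 45% | 8-26% |
| By organ, arms pooled | 45% | 0.3-3% |
| By irradiated site, 3-5 strata | 45% | 99.6-100% |
| By irradiated site, 3-5 strata | 20% | 28-91% |
| Any site, SBRT arm | 20% | 8-20% |

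**Sensitivity.** These ranges also include a Beta(0.5,0.5) prior and, unless stated otherwise, other interim schedules.
- Pooled, 45% with SBRT: 35-73% with controls at 10% and 62-86% with controls at 17%. At a final look only, 9% and 34%.
- By organ in the SBRT arm: 4-28% when looks start at patient 6 or later, 17-69% when they start at patient 1, and about 0% at a final look only.

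**Run-in as a backstop.** If 45% is taken as its event rate, with at most one event per patient, Pr(at least 4 of 6) = 15(0.45⁴)(0.55²) + 6(0.45⁵)(0.55) + 0.45⁶ = 0.186 + 0.061 + 0.008 = 25.5%.

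**The case against.** The strongest reply is that site most naturally means the treated or metastatic site. The protocol uses the word that way in the eligibility criteria (5.1.4, 5.2.3), the treatment and follow-up sections (6.2, 6.3) and the lesion definitions (11.3), while Section 15.6 summarises adverse events by type and grade. On that reading controls have no irradiated site, dilution disappears, and a true 45% is almost always detected. This stands. A reader might infer that the rule as written is bound to miss excess toxicity; the documents do not support that. On this reading the fault runs the other way, towards false suspension.

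The pooling is also an inference. Sections 11.2 and 15.7 say who is evaluable for safety, and Section 15.4 does not cite them. A reader should not conclude that the sponsor intends to combine the arms, only that nothing in the text prevents it.

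The 45% rate and its even split over three organs are assumptions. One dominant organ, or patients with events in several organs, would raise the per-organ rates and narrow the gap. So would a higher control rate or looks from the first patient.

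Finally, Section 15.4 is not the only protection. The Safety Monitoring Committee (Section 13), reporting to the IRB (12.5.2) and the individual removal and discontinuation criteria (6.6, 8.2) also operate. None of these sets a numerical limit on the SBRT arm's rate, so the gap remains.

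**Conclusion.** The point holds as a conditional one. Section 15.4 leaves site, arm and denominator undefined, and none of the three readings examined gives a dependable test of the combination against the 30% limit. With arms pooled or toxicity split by organ, an assumed true 45% is suspended in between 0.3% and 47% of trials, against about 99% for an any-site SBRT-arm rule. With irradiated-site strata, detection is near certain, but 28-91% of trials are suspended at a true 20%. These figures rest on the assumed rates, three priors and looks every 10 patients, because the plan supplies none of them. The boundary result, 40/73 events with SBRT passing when controls have 7/73, depends on neither the simulation nor the assumed true rates. This should be corrected, since it concerns the main numerical safeguard after the sixth patient.

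**What to change.** Keep the sponsor's 30% and 75% limits and amend Section 15.4 as follows.

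1. Make the primary trigger the proportion of patients who started SBRT with at least one grade 4/5 event at any site, with patients who started SBRT as the denominator.
2. Define site, and state the prior, the first look and the look schedule.
3. Report site-specific rates and the CBI-alone rate at each review.
4. Keep a site-specific trigger only with a stated minimum number of patients per site and with its operating characteristics reported. Left as it is beside the new rule, it would bring the over-triggering with it.

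The cost is a wording amendment and a short simulation; events of grade 3 or higher are already collected (Sections 12.1 and 12.2.1). The downside is some unnecessary reviews. At a true 20%, the any-site SBRT-arm rule suspends in about 8-20% of trials with looks every 10 patients, and in about 15-47% with a look after every patient. The look schedule should therefore be chosen with these figures in view.
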